5.8. Randomisation

Patients who consent to the study and agree to randomization will be randomized to either intervention or control group. We propose individual level randomisation to intervention or usual care, with stratification according to the prior duration of illness (> 7 days or less than 7 days).

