1. OVERVIEW OF RESEARCH

Design: Pilot RCT

Target population: Adults with uncomplicated acute rhinosinusitis: acute sinus discomfort (<=4 weeks), and 2 of reported nasal obstruction, reported purulent discharge, or pus visible).

Trial groups: a) Immediate antibiotics (this approximates usual care: currently nearly 95% of patients receive antibiotics) b) advice to use high volume hypertonic saline nasal irrigation with a delayed prescription for antibiotics.

Baseline measures: Structured history/examination. Nasal swabs for bacteriology (optional to maximise participation).

Feasibility outcomes: follow-up rates, recruitment rates, adherence/acceptability of the intervention. **Primary outcome**: Antibiotic use.

Other outcomes: duration of moderately bad symptoms (using a validated symptom diary; variables (using 7 point Likert scales): nasal blockage, discharge, unpleasant taste/smell, facial pain, pain on bending, impaired activities, generally unwell, sleep disturbance.

Secondary outcomes: symptom duration until little/no problem; mean symptom score; development of new/worsening symptoms. Health related quality of life (EQ5D). Reconsultations/resource use during the next month.

Sample size: Feasibility estimates: to estimate follow-up rates in each group between 65% and 80% assuming we want to be reasonably sure that the follow-up rate is not 50% in each group (i.e.95% confidence intervals of +/- 15%) then 41 per group are needed. We also anticipate that it should be possible for the intervention group to achieve use of antibiotics of around 65% or less. To estimate this proportion with 95% confidence intervals of +/- 15% (i.e. that antibiotic use is 80% or less) 41 per group is also needed. To allow for loss to follow-up more than 100 patients are needed.

Feasibility. Our previous JAMA trial recruited 238 individuals/4 years with one RA (one centre), but recruitment is currently more challenging. We therefore estimate that with one RA at the coordinating centre and P/T RAs in two other centres will allow us to recruit our target efficiently in 2 winter seasons

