5.4. Inclusion criteria

Inclusion criteria

We will pragmatically define acute sinusitis as having sinus discomfort, and at least 2 other symptoms (2 of: patient reported nasal obstruction, patient reported purulent nasal discharge, or pus seen in the nasal cavity on inspection by the clinician). We do not propose using prior duration (e.g. the requirement for at least 7 days without improvement in the Canadian guidelines) since there is no good evidence for a particular cut-off, and our aim is to help people who are currently being treatment with antibiotics for sinusitis, many of whom present with 7 days.

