9. STATISTICS

9.1. Description of Statistical Methods

The pilot data will examine organisational difficulties, whether fewer than expected eligible patients were recruited, any issues reported by GP regarding patients eligibility, and concerns encountered from patients.(28) Unearthing the key problems for recruiters is of central importance in the piloting phase and we anticipate that the issues will become apparent, as they have in our previous studies, in the process of detailed and sensitive discussion/iteration between an experienced trial manager and the 20-30 recruiting clinicians who are likely to participate in piloting. Based on this we would then make any required adjustments to the recruitment procedures, but no forma statistical analysis will be undertaken.

Statistical analysis.

Analysis of the feasibility outcomes will be descriptive with 95% confidence intervals provided for all proportions of interest, and where relevant also subdivided by trial group (e.g. proportion followed-up; proportion of the intervention group using nasal irrigation, proportion in each group using antibiotics).

We will also provide a table of baseline characteristics by trial group also presented with their 95% confidence intervals, and a similar table of outcomes at follow-up in each trial group for all clinical outcomes with their 95% confidence intervals.

We will do an exploratory intention to treat analysis, blind to group allocation, of the difference in antibiotic use between trial groups using logistic regression controlling for the severity of baseline symptoms, and other potential confounding variables as appropriate. Analysis of duration of symptoms will be performed using Cox proportional hazard models, again controlling for baseline covariates. Kaplan Meier curves will be used to demonstrate the resolution of symptoms graphically. Analysis of symptom severity will use linear regression modelling controlling for baseline covariates.

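### The randomisation strata leave out exactly 7 days of illness, and the analysis section does not require the stratification factor in any model

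*Protocol*

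**What the plan says.** Section 5.8 of the protocol randomises individuals with "stratification according to the prior duration of illness (> 7 days or less than 7 days". No other factor is used, and no other section says where a duration of exactly 7 days belongs.

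Such patients can enter. The overview (section 1) admits "acute sinus discomfort (<=4 weeks", and section 5.4 sets no minimum: "We do not propose using prior duration". The same section says of the patients it wants to reach, "many of whom present with 7 days" (possibly a slip for within 7 days).

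Section 9.1 plans three models:

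- Antibiotic use: "using logistic regression controlling for the severity of baseline symptoms, and other potential confounding variables as appropriate".
- Symptom duration: "Cox proportional hazard models, again controlling for baseline covariates".
- Symptom severity: "Analysis of symptom severity will use linear regression modelling controlling for baseline covariates".

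Prior duration and the randomisation stratum are not named in section 9. Section 9.1 describes the between-group comparison as exploratory, and section 9.2 sets a 5% significance level.

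**The concern.** There are two linked weaknesses.

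First, the allocation rule is incomplete. One week is a natural duration for a patient to report, so the missing value is not a remote case. Someone has to place these patients, and the protocol does not say where. A statistical analysis plan cannot repair this once patients have been allocated.

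Second, the trial balances on prior duration but does not commit to using it in the analysis. The criterion in 9.1 for adding covariates is potential confounding. A factor balanced by design will tend not to look like a confounder, so a literal reading could drop the only stratifier. At stake is some efficiency in the exploratory comparisons, and an incomplete stratum definition that could be carried into the main trial this pilot is meant to inform.

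**Working it through.** **Step 1: coverage of the strata.** Eligible durations run up to 4 weeks with no minimum (sections 1 and 5.4). The strata are below 7 days and above 7 days, so 7 days itself is unassigned. The protocol does not give the share of patients at that value. If it were 5% to 20% (an assumption), the count would be 0.05 × 108 ≈ 5 to 0.20 × 108 ≈ 22 patients.

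**Step 2: the plan's own sample size.** Section 5.15 gives 90% versus 65%, alpha 0.05 (taken as two-sided), 80% power and 20% loss. With pooled variance and no continuity correction, mean proportion 0.775:

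n = [1.960 × √(2 × 0.775 × 0.225) + 0.842 × √(0.90 × 0.10 + 0.65 × 0.35)]² / 0.25² = 42.6, so 43 per group.

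43 / 0.80 = 53.75, so 54 per group and 108 in total. Both stated figures reproduce, and nothing in this point changes them.

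**Step 3: effect of omitting the stratum from the logistic model.** Logistic likelihood-ratio tests were simulated with 86 analysed patients (2 × 43), two equal strata balanced by arm, and 4,000 runs per setting. Baseline severity was not modelled. Type I error was taken with both arms at 77.5%, and power at 90% versus 65%. The stratum odds ratio for antibiotic use is assumed.

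| Stratum odds ratio | Type I error, unadjusted / adjusted | Power, unadjusted / adjusted |
|---|---|---|
| 1 | 4.9% / 5.0% | 82.2% / 82.6% |
| 2 | 4.7% / 5.0% | 82.3% / 84.0% |
| 3 | 4.8% / 5.5% | 82.6% / 84.9% |
| 5 | 3.7% / 5.0% | 82.2% / 86.3% |
| 10 | 3.7% / 5.2% | 83.2% / 89.0% |

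The simulation error is about √(0.05 × 0.95 / 4000) = 0.3 points for the type I error, so the 5.5% is compatible with 5%. Power lost by omission is about 0 to 2 points at odds ratios of 1 to 3, and about 4 to 6 points at 5 to 10.

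**Step 4: does omission widen the intervals?** For the logistic model it does not. With both arms at 77.5%, the unadjusted standard error of the treatment log odds ratio is √[2 / (43 × 0.775 × 0.225)] = 0.516. With the stratum in the model it is 1 / √[10.75 × (w₁ + w₂)], where w is p(1 − p) in each stratum and 10.75 = 43/4. This gives 0.522, 0.529, 0.542 and 0.562 at stratum odds ratios of 2, 3, 5 and 10. Adjustment raises the standard error slightly; the power gain comes from the conditional estimate moving further from zero.

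For the linear model, omission does widen the interval, by 1/√(1 − R²): a factor of 1.054 at R² = 0.10 and 1.118 at R² = 0.20. Both R² values are assumed, and they mean variance not already explained by baseline severity. They should not be carried over to antibiotic use, where at 77.5% overall a binary stratum needs an odds ratio of about 5.4 to explain 10% of the variance and about 17.6 to explain 20%.

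**The case against.** The strongest reply is that 9.1 does not exclude the stratifier. Prior duration is a baseline covariate, the wording allows it in every model, and a full covariate list is commonly left to a statistical analysis plan, which may exist. That stands as far as it goes: the protocol permits the adjustment, and an unseen plan may already set it. But 9.1 does name one covariate, and it makes the rest depend on confounding, which is the wrong test for a factor balanced by design. The reply does not touch the gap at 7 days, which belongs to the allocation rule.

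It is also fair that little hangs on the result. The feasibility outcomes are descriptive, the group comparison is exploratory, and omission errs on the conservative side.

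A reader might infer more than the document supports:

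- That all unadjusted intervals would be 5% to 12% too wide. This is the linear-model factor; for the logistic model the standard error moves the other way, and no such figure was derived for the Cox model.
- That the stratifier was chosen because it predicts outcome. The protocol gives no reason for the choice.
- That sites will classify day-7 patients inconsistently. The protocol does not say how strata are assigned, and a coded system could apply one rule throughout.
- That the gap biases the comparison. A day-7 patient placed in either stratum is still randomly allocated.

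**Conclusion.** The point holds in a limited form. The strata in 5.8 are not exhaustive as written, which is a plain drafting error in an allocation rule. Section 9.1 leaves adjustment for the stratum optional, which is a missed and nearly free improvement rather than an invalid analysis.

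The cost of omission for antibiotic use is negligible to small (up to about 2 points of power) if the stratum odds ratio is 3 or less. It becomes noticeable (4 to 6 points, with a type I error near 3.7%) only at odds ratios of 5 to 10. These sizes rest on assumed odds ratios, equal strata, 86 analysed patients and no other covariate in the model. The effect on the Cox analysis of symptom duration was not quantified. The change is worth making, but the trial's conclusions do not depend on it.

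**What to change.** In section 5.8, make the two strata exhaustive by assigning exactly 7 days to one of them. Either side will do, provided the text matches what the randomisation system applies. If recruitment has begun, state the rule actually used.

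In section 9.1, include the randomisation stratum as a fixed covariate, alongside baseline symptom severity, in the logistic, Cox and linear models. Use this in place of the open reference to other potential confounders, or list any further covariates in advance.

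The cost is two wording changes, one check of the randomisation set-up and one degree of freedom per model. The sample size remains 108.

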5.9. Pilot phase

This is the protocol for the pilot phase: if successful we will apply to the HTA or other funding bodies to fund the main trial.

5.10. Eligible patients not recruited to the trial

Some patient will decline participation. The main concern for the trial data is that due to selection bias the trial may end up having limited generalisability. Hence we propose that GPs record reasons for non-participation where feasible to do so.

5.11. Data Collection - Measurements and follow-up

Nasal sampling (swabs to send for bacteriology/virology) will be optional to maximise the generalisability of the sample, but we envisage from our experience of the TARGET cohort and other studies a high level of acceptance of sampling (at least 80%). The key microbiology of interest is the bacteriology for the common bacterial pathogens since we are interested in exploring whether the presence of pathogens predicts response to antibiotics but we will also aim to store the viral samples for future analysis. Participants will keep a diary of symptoms and daily activities (including days away from work) for up to four weeks after inclusion, and will post the diary back once symptoms have settled. If no diary is received a brief questionnaire will be sent to document the key outcomes (antibiotic use; severity and duration of symptoms), and following this a phone call and/or text to individuals not returning the brief questionnaire.

5.12. OUTCOMES Proposed feasibility outcomes.

- Recruitment rate
- Proportion of eligible patients who accept randomisation
- Proportion using nasal irrigation in the first week in the intervention group
- Proportion using their antibiotic prescription in the intervention group and in the control group
- Proportion followed up with a primary outcome in each group

Proposed clinical outcomes

Antibiotic use: Use of antibiotic prescriptions reported in the 4 weeks of the symptom diary. We anticipate that the intervention will help individuals both decide not to use an immediate prescription if they have been given one and particularly limit the redemption of any delayed prescription. We have shown that the use of delayed prescriptions reported in diaries matches whether they were collected from practices(17).

Secondary outcomes

- Duration of moderately bad illness. The duration of illness rated moderately bad or worse i.e. making an important difference to patients, and as used in our previous studies of respiratory infections (20, 21). It will be measured using the symptom diary and where the diary is not returned information from a brief follow-up questionnaire, and/or phone call as necessary. The 4 week diary includes 11 symptom variables, assessed on 7 point Likert scales. The score has been developed to have content validity by incorporating items which not only take account of proposed diagnostic criteria for bacterial rhinosinusitis(22) but also physicians' perceptions of the important clinical features (based on focus groups and a questionnaire study)(23). The format of the diary items has been developed in a variety of other respiratory infections and been shown to have construct and criterion validity, and also sensitivity to change.(8, 17, 24) We have also shown the total symptom score for sinusitis is internally reliable (Cronbach's alpha 0.77) and sensitive to change (standardized response mean 1.6 comparing day 0 with day 5).(8, 24)
- The duration of any symptom until rated very little or no problem (measured as above);
- **Reconsultation** with non-resolving, new, or worsening illness within 1 month of the index consultation documented from medical records, and which can be measured reliably(25);
- EQ5D5L (at days 1,7,14,21,28 of the diary). In prior trials EQ5D has been shown to be adequate in detecting the decrement in QOL with RTIs to allow cost-effectiveness modelling(26) should the main trial be funded;
- **Resource use.** Information on NHS resource usage will be collected for all participants from a notes review including capturing resource use for rare major adverse events (e.g. anaphylaxis, complications, hospital admission) up to 28 days.

- Self-reported adherence and reasons for non-adherence, using the validated Problematic Experiences of Therapy Scale, across different aspects of intervention materials (written / video / online instructions).
- Modified Patient Enablement Instrument(27)

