6.5. Concomitant Medication

Trial participants will be advised to continue their usual regular medications while taking part in the trial. Healthcare professionals will record data at baseline on antibiotic prescriptions given during the consultation, also any other prescriptions (e.g. inhalers, analgesics). We will advise clinicians to prescribe an appropriate betalactam antibiotic when prescribing as a first line agent (unless allergic to beta-lactams in which case a macrolide will be advised).

Patients will be advised that they can take over the counter medications for their sinusitis (e.g. analgesics). They will be asked to record these additional medications in the study diary from days 1 to 28.

Clinicians will treat trial participants who re-consult in whatever way they feel is clinically appropriate.

A member of the research team will provide the practice staff with instructions for extraction of data and a form to record the data from participants' medical notes on further antibiotics and other medications prescribed during the 28-day period after study entry.

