8. HEALTH ECONOMICS

We do not propose a formal Economic analysis for the feasibility study, but simply feasibility wok to ensure that cost/resource data can be collected.

We will measure the quality of life based on the EQ5D5L. The EQ5D5L will be included on the basis that it measures quality of life at a point in time, and will be used in conjunction with the clinical outcome measures at days (1,3,7,14,21,28). This is important for an acute condition, and EQ5D was very helpfully used in the GRACE studies in adults to document change over time (and did change significantly which suggests it is likely to be useful in this population too).

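### Posting the diary back when symptoms settle conflicts with the 4-week antibiotic outcome and the day-21 and day-28 EQ-5D; first antibiotic use after settling can be missed, more often in the delayed-prescription arm

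*Protocol*

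**What the plan says.** Section 5.11 has participants keep the diary for at most four weeks, and says that they "will post the diary back once symptoms have settled". If no diary arrives, a brief questionnaire is sent, followed by a call or text to those who do not answer it. No contact is planned for someone whose diary arrives early.

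Three items need the diary for a fixed 28 days:

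- Antibiotic use. Section 1 states "Primary outcome: Antibiotic use", and section 5.12 defines it as "Use of antibiotic prescriptions reported in the 4 weeks of the symptom diary".
- Quality of life. Section 5.12 lists "EQ5D5L (at days 1,7,14,21,28 of the diary"). Section 8 gives a different schedule, alongside the "clinical outcome measures at days (1,3,7,14,21,28"), which adds day 3.
- Over-the-counter medication. Section 6.5 says "They will be asked to record these additional medications in the study diary from days 1 to 28".

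Separately, sections 6.5 and 7 describe a review of medical notes for further antibiotics prescribed in the 28 days after study entry. Nothing says that these data feed into the antibiotic outcome.

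**The concern.** A diary that has been posted cannot record later days. Someone who settles on day 10 and posts then leaves 18 of the 28 days unobserved, yet could count as followed up with a primary outcome, which is itself a feasibility result of this pilot. The record would show a non-user rather than a missing value, so neither the follow-up rate nor the imputation foreseen in section 9.3 would reveal the gap.

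The gap is uneven between arms. Controls receive an immediate prescription and most become users at once; a recorded user cannot be misclassified by anything that happens later. Only people still recorded as non-users when they post can be, and these are mostly in the delayed-prescription arm, where some may still hold an unused prescription. The error would therefore run in favour of the pilot's hypothesis.

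For EQ-5D-5L, the people who drop out of the day-21 and day-28 assessments are those who have recovered. Missingness then depends on health state in both arms, and no settled participant who has posted supplies a late value from which others could be imputed.

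**Working it through.** **Inputs.** Section 5.15: control use 90%, intervention use 65%, alpha 0.05 (two-sided assumed), power 80%, 43 per group, 20% loss, 108 in total. Section 3: median illness of 2 weeks in a UK primary care trial and nearly 3 weeks in a systematic review (taken as 3).

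**1. The plan's own figure.** Two-proportion formula with pooled variance and no continuity correction; mean proportion (0.90 + 0.65)/2 = 0.775:

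n = [1.96 × √(2 × 0.775 × 0.225) + 0.842 × √(0.90 × 0.10 + 0.65 × 0.35)]² / 0.25² = 42.6, so 43 per group. Then 43/0.80 = 53.75, so 54 per group and 108 in total. The figure reproduces and is not affected by this point.

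**2. Who can be misclassified.** Expected non-users among those analysed:

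- control: 43 × 0.10 = 4.3
- intervention: 43 × 0.35 = 15.05

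**3. Illustration of the effect on the difference.** The documents give no rate of first use after posting. If a share s of non-users in each arm starts an antibiotic after posting, the overstatement is (15.05 − 4.3) × s / 43 = 0.25 × s. For each 10% this is 3.5 points missed in the intervention arm and 1.0 in the control arm, a net 2.5 points against the 25-point target.

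The 10% applies to all non-users. If only 50-75% of them have settled and posted (step 5), it implies that 0.10/0.75 = 13% to 0.10/0.50 = 20% of those who posted go on to start an antibiotic.

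**4. What a given loss would do to the test.** At 43 per group, with the loss in the intervention arm only:

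| Points missed | Apparent reduction | Chance of a significant result |
|---|---|---|
| 0 | 25 points | 80.4% |
| 2 | 27 points | 85.3% |
| 5 | 30 points | 90.9% |

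These rows show sensitivity and are not estimates.

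**5. EQ-5D-5L.** Assume exponential time to settling from inclusion, with the section 3 medians. Share settled by day d = 1 − 0.5^(d/median):

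| Day | Median 14 days | Median 21 days |
|---|---|---|
| 21 | 65% | 50% |
| 28 | 75% | 60% |

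These are the shares that could have posted the diary before the assessment fell due.

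**The case against.** The strongest reply is that little antibiotic use would escape. Section 5.7 ties use of the delayed prescription to symptoms that are clearly worsening or not starting to settle after a further week. Such a participant has not settled and still holds the diary. This stands. A reader might infer that later antibiotic use in general is lost, but the documents do not support that: the gap is limited to first use after settling, through relapse, a new illness, or a retained prescription taken later.

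A new prescription at reconsultation would also appear in the notes review. That too stands, but it does not close the gap. The outcome is defined by diary report, and a prescribing record does not show whether a prescription offered at baseline was later taken.

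A reader might also take the feasibility item, "Proportion using their antibiotic prescription in the intervention group and in the control group", as a second and narrower version of the primary outcome. It belongs to a separate list and can be read as uptake of the prescription issued at entry, so it does not show that the clinical outcome excludes new prescriptions.

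Finally, the protocol elsewhere speaks of a four-week diary and of recording on days 1 to 28, and the diary's own instructions are not shown. Some recovered participants may keep it to the end. It is therefore too strong to say that late EQ-5D-5L can exist only for people who are still ill. What is established is that the sections conflict and that section 5.11, followed as written, produces the gap.

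**Conclusion.** The point holds as a conflict within the protocol. The return-when-settled rule cannot be squared with a four-week antibiotic window, EQ-5D-5L on days 21 and 28, or medication recording to day 28, and the back-up contact does not reach early returners.

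For the antibiotic outcome, the direction is clear at the planned rates, provided that late starting is not much commoner among control non-users: about 15 intervention against 4 control participants are open to misclassification, so an undercount favours the intervention. The amount is unknown. The 2.5 points per 10% is conditional arithmetic, and no specific bias should be read from it.

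For EQ-5D-5L, late values would come mainly from unrecovered people in both arms. The 50-65% and 60-75% rest on an exponential course and on medians from other studies applied from inclusion.

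This should be fixed but is not critical. The between-group comparison is called very provisional (5.15) and exploratory (9.1), no cost-effectiveness analysis is planned (5.14), and the sample size is unchanged. It still merits action because the pilot is meant to estimate antibiotic use and follow-up for a full trial, which could inherit the rule. The day-3 mismatch between sections 5.12 and 8 is minor.

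**What to change.** - In section 5.11, keep the antibiotic and EQ-5D-5L items in the diary to day 28 for everyone; daily symptom items may stop at resolution. Alternatively, let participants post early and send early returners one text or call at day 28 with these items.
- In section 5.12, define the outcome as any antibiotic taken within 28 days, from any prescription.
- State that the further antibiotics already extracted from the notes (6.5 and 7) supplement the self-report in the same way in both arms, bearing in mind that they show prescribing and not use.
- Bring section 6.5 into line with the diary rule, and give one EQ-5D-5L schedule in sections 5.12 and 8.

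The cost is a change to the diary instructions and outcome wording, or one short contact per early returner. The downsides are slightly more burden on recovered participants and possibly later diary return. No extra participants are needed. Analysis cannot recover days that were never observed, so the change has to be made in data collection.
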